## RUN;

In the event of gross violations from the normality assumptions (identified using the shape of the distribution and QQ plots of change from baseline overall) or in case of convergence criterion fails to be reached, a non-parametric analysis will be used instead: the same model will be performed on ranked data using the following SAS® code:

PROC RANK data = ADFT(where = (paramcd="ROMxx" AND ittfl="Y")) out = RANK;

BY avisitn;

VAR chg base;

RANKS chg\_r base\_r;

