10.2 Sample Size Determination

The sample size was determined based on the primary efficacy endpoint (percentage of responder subjects at Week 6 after the second injection according to composite AROM). A 60% response rate was assumed based on previous studies (adult UL/LL) with an additional benefit of $\pm 10\%$ compared with that observed in these studies (approximately 50% response rate at Week 4 of Cycle 2). The aim of this study will be to estimate this proportion with an accuracy of $\pm 8\%$. Given a two-sided 95% confidence interval (CI), 145 subjects are required; with an assumed 5% dropout rate, 153 subjects will have to be enrolled to achieve a target of 145 evaluable subjects (i.e. subjects included in the mITT population). These calculations have been performed with nQuery using CI for proportions and assuming normal approximation.

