- subject compliance with the GSC: percentage of days over study period when GSC therapy was performed (as determined from the subject diary)
- global assessment of benefits, evaluated by both the investigator and the subject (or caregiver): at the end of each cycle
- in subjects with an injection planned at Week 16 or 20 of each cycle satisfaction with longer interval collected at the corresponding reinjection visit or the last cycle visit.
- quality of life changes, measured on the EQ-5D 5L and SF-12 scales: change from baseline to Final Visit.

Analysis of the Secondary Efficacy Endpoints

The secondary efficacy endpoints will be summarised descriptively at each relevant visit using the safety/ITT population. Unless otherwise specified, missing values will not be imputed.

Additionally, adjusted mean change from baseline in AROM variables at each relevant postbaseline timepoint and associated two-sided 95% CIs will be estimated from an analysis of covariance (ANCOVA) model with primary TT and country as fixed effects and the appropriate baseline AROM value as covariate. Active UL and LL functions and quality of life questionnaires will be summarised in a similar way as AROM variables.

Percentage of responder subjects at Week 6 after the first injection, according to composite AROM in the primary TT limb, will be analysed in a similar way as for the primary efficacy endpoint.

Using the total number of study days and the total number of days when GSC therapy was not performed (as recorded in the eCRF from the subject diary), the number of days when GSC was performed will be calculated. This percentage of days over the study period when GSC therapy was performed will be calculated by subject and summarized descriptively as a categorical ordinal variable.

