# RUN;

PROC MIXED data = RANK method=reml;

BY avisitn;

CLASS limb countryc;

MODEL chg\_r = limb countryc base\_r / DDFM=kr;

LSMEANS limb countryc / ALPHA=0.05 CL;

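### When normality looks doubtful, the SAP replaces the secondary ANCOVAs with a rank model that cannot give the promised adjusted mean change, and it checks raw change, not residuals

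*SAP*

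**What the plan says.** Protocol 10.4.5.2 plans descriptive summaries of the secondary endpoints and, in addition, "adjusted mean change from baseline in AROM variables at each relevant postbaseline timepoint and associated two-sided 95% CIs", estimated from an ANCOVA with primary target limb, country and the baseline value. SAP 3.2.1.2 repeats this for AROM in each of the ten muscle groups, with an adjusted mean change and 95% CI for each primary target limb and a p-value for each fixed factor.

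The SAP then adds a fallback. If normality is grossly violated ("identified using the shape of the distribution and QQ plots of change from baseline overall"), or if the model does not converge, "a non-parametric analysis will be used instead: the same model will be performed on ranked data". The code ranks the change and the baseline within each visit, refits the model to the ranks and requests "LSMEANS limb countryc / ALPHA=0.05 CL". It gives no back-transformation and no other estimate in original units.

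Composite and full composite AROM, MFS, walking speed, EQ-5D-5L and SF-12 are all referred back to this analysis, so the fallback reads as carrying over to them. The protocol has no such fallback, and SAP section 5 (changes from protocol) does not list it.

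**The concern.** There are two separate problems.

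- **Replacement.** The study has one arm, so the level of change from baseline is its measure of effect. A rank expresses each subject's change only relative to other subjects' changes, so the level drops out. The planned single-muscle-group ANCOVA table is titled in degrees, but its adjusted means would be ranks.
- **Trigger.** ANCOVA assumes normal residuals given limb, country and baseline. The SAP looks at the change itself. Its word for this is overall, and in the MFS and walking-speed paragraphs it sets that word against a split by primary target limb, so I read it as pooled. A limb difference or a skewed baseline can make raw change look non-normal when the model is sound. A strong, normally distributed baseline effect can hide badly skewed residuals.

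At stake is the adjusted estimate for any secondary variable that trips the rule. This is not far-fetched for the EQ-5D-5L items: each has five levels, so its change is discrete.

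**Working it through.** **Number of subjects.** Protocol 10.2 plans 145 evaluable subjects for a 60% response rate, a half-width of 8 points and a 95% CI by normal approximation. n = 1.96² × 0.60 × 0.40 / 0.08² = 144.05, rounded up to 145. 145 / 0.95 = 152.6, rounded up to 153. Both figures reproduce, and the half-width at 145 is 7.97 points. I use n = 145 below.

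**What the rank model can return.** For n subjects at a visit, the mean rank is (n + 1)/2, here 146/2 = 73.0, whatever the true change. If a constant c is added to every change, all orderings stay the same, so the ranks, LS means, CIs and limb p-value stay the same. This is algebra and needs no distributional assumption.

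**Illustration.** The documents give no AROM mean or SD, so these inputs are assumptions: one set of 145 (73 upper, 72 lower limb), four countries, baseline normal with mean 100 and SD 20, baseline slope -0.1, upper-limb effect 2, and exponential errors with SD 12. A constant was then added to every change.

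| Constant | Mean change | Adjusted mean LL, degrees (95% CI) | Adjusted mean UL, degrees (95% CI) | Rank LS mean LL | Rank LS mean UL |
|---|---|---|---|---|---|
| -10 | -9.84 | -10.17 (-12.95 to -7.39) | -9.54 (-12.33 to -6.76) | 68.53 | 76.95 |
| 0 | 0.16 | -0.17 (-2.95 to 2.61) | 0.46 (-2.33 to 3.24) | 68.53 | 76.95 |
| +10 | 10.16 | 9.83 (7.05 to 12.61) | 10.46 (7.67 to 13.24) | 68.53 | 76.95 |
| +30 | 30.16 | 29.83 (27.05 to 32.61) | 30.46 (27.67 to 33.24) | 68.53 | 76.95 |

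The rank CIs (58.97 to 78.10 and 67.38 to 86.53) and the rank limb p-value (0.2185) were the same in all four rows.

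**Trigger.** I compared raw change with residuals by a Shapiro-Wilk test at 5%: n = 145, residual SD 10, 2000 runs per case, limb and baseline in the model, country left out.

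| Case | Raw change flagged | Residuals flagged |
|---|---|---|
| Normal errors, limb difference 0 | 5% | 5% |
| Normal errors, limb difference 1 SD | 4% | 5% |
| Normal errors, limb difference 2 SD | 15% | 5% |
| Normal errors, limb difference 3 SD | 91% | 6% |
| Normal errors, skewed baseline, slope 1 SD | 71% | 6% |
| Normal errors, skewed baseline, slope 2 SD | 99.8% | 5% |
| Exponential errors, normal baseline, slope 2 SD | 13% | 100% |
| Exponential errors, normal baseline, slope 3 SD | 6% | 100% |

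Slopes are in residual SDs per baseline SD. The check on raw change can err both ways, or hardly at all, depending on the case.

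**Is the replacement needed?** With exponential errors (SD 12), 73 and 72 subjects per limb group and 5000 runs, the ordinary 95% CI for the upper-limb adjusted mean covered the truth in 94.9%.

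**The case against.** The strongest reply is that little is lost.

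- A reader might infer that a variable which trips the rule is left with no change from baseline in its own units. The documents do not support that. The objectives do not mention adjustment, the AROM, MFS and walking-speed endpoints are mean changes, and the protocol offers the adjusted means only as an addition. SAP 3.2.1.2 presents unadjusted changes with 95% CIs without any normality condition, and SAP 3.2.16 adds medians and quartiles.
- A reader might also infer that the rank model is useless. It is not. The SAP describes the ANCOVA as comparing upper with lower limb as primary target, and ranks still test that contrast. The invariance concerns shifts common to all subjects; if only one limb group improves, the rank output changes.
- The flag rates above are not the rate at which the fallback would be used. The SAP relies on a visual judgement of gross departure, not a formal test, and the scenarios are assumed. Every subject is injected in both limbs, so nothing in the documents points to a limb difference of 2 or 3 residual SDs.
- Model-checking output goes into the statistical appendix. That helps a reader, but the stated switch does not use it.
- With no random or repeated effects in the model, the non-convergence trigger is unlikely to matter.

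All of this limits the consequence. It does not alter the fact that the rank analysis is specified as a substitute, or that the trigger inspects the wrong quantity.

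**Conclusion.** The point stands in a narrow form. Once triggered, the fallback cannot deliver the covariate-adjusted mean change with 95% CI that the protocol and the SAP promise, and nothing else in either document restores it. That part holds without any distributional assumption. The trigger can err in either direction; how often cannot be stated, because the documents give no AROM means, SDs or baseline shapes.

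The loss is confined to adjusted estimates for secondary, descriptive endpoints with exploratory p-values. The primary responder analysis is unaffected. The change is worth making because it is cheap and restores a promised estimate, not because the main result is at risk.

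**What to change.** In SAP 3.2.1.2:

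1. Judge normality on the residuals of the fitted ANCOVA, not on raw change.
2. Always report the ANCOVA adjusted mean change in original units. If residuals are grossly non-normal, give a bootstrap or sandwich 95% CI, with the choice named in advance.
3. Keep the rank model only as a supportive test of the limb factor, labelled as such, and not as a replacement.
4. State that the same rule applies to composite and full composite AROM, MFS, walking speed, EQ-5D-5L and SF-12.

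Medians need no new request, since SAP 3.2.16 already requires them. The cost is SAP wording and a few lines of SAS, with no new data and no change to the sample size.

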# RUN;

PROC MIXED data = RANK method=reml;

BY avisitn;

CLASS limb countryc;

MODEL chg\_r = limb countryc base\_r / DDFM=kr;

LSMEANS limb countryc / ALPHA=0.05 CL;

## RUN;

All the SAS outputs produced during the analyses and the model checking procedures will be included without reworking the data (raw output) in the statistical appendix.

# Composite AROM against injected muscle groups (any of the 10 prespecified), in upper and lower limbs

Summary statistics (including the two-sided 95% CI) will be presented for raw values and changes from baseline at each relevant visit: baseline (for raw values only), Week 6 and Week 12 of injection cycle 1, re-injection cycle visit, Week 6 and Week 12 of injection cycle 2, and last study visit.

The change from baseline of composite AROM against each injected muscle group between the upper limb and the lower limb as primary TT will be analysed in the same way as AROM against 10 prespecified muscle groups.

# Full composite AROM against five UL muscle groups or full composite AROM against five LL muscle groups or overall full composite AROM against ten prespecified muscle groups

The full composite AROM against five UL muscle groups, the full composite AROM against five LL muscle groups and the overall full composite AROM against ten prespecified muscle groups will be summarised and analysed in the same way as composite AROM against injected muscle groups.

# • Active UL function

Summary statistics (including the two-sided 95% CI) will be presented overall and by primary TT limb for raw values of the MFS overall scores, assessed locally and centrally by a reviewer blinded regarding the order of the video recording/visit number for a given subject, at baseline, Week 12 of each injection cycle and last study visit, as well as for the change from baseline at Week 12 of each injection cycle and last study visit.

For the MFS overall scores, assessed locally and centrally by a reviewer blinded, the change from baseline between the upper limb and the lower limb as primary TT will be analysed at Week 12 of each injection cycle and last study visit using the same model as AROM against 10 prespecified muscle groups.

The concordance between the results from the local assessment by the investigators and from the central review will be evaluated. For each analysed visit, the Lin's concordance correlation coefficient [9] and the associated two-sided 95% CI will be calculated on the raw data. The Brand-Altman graph will also be presented.

The Lin's concordance correlation coefficient and the associated two-sided 95% CI will be calculated using the macro mccc.sas (http://bioinformaticstools.mayo.edu/research/mccc/).

# • Active LL function

Summary statistics (including the two-sided 95% CI) will be presented overall and by primary TT limb for raw values of the maximal WS barefoot (m/s) at baseline, Week 12 of each injection cycle and last study visit as well as for the changes from baseline at Week 12 of each injection cycle and last study visit.

For the maximal WS barefoot, the change from baseline between the upper limb and the lower limb as primary TT will be analysed at Week 12 of each injection cycle and last study visit using the same model as AROM against 10 prespecified muscle groups.

# • Subject's satisfaction with the GSC

Summary statistics (including the two-sided 95% CI) and frequency tables will be presented for raw scores at each relevant visit:

- Baseline (for non-naïve subjects to GSC only),
- Week 6 and Week 12 of injection cycle 1,
- Re-injection cycle visit,
- Week 6 and Week 12 of injection cycle 2,
- Last study visit.
- Subject's beliefs that the GSC will help to improve functional capacity

Summary statistics (including the two-sided 95% CI) will be presented for raw scores and changes from baseline at each relevant visit: baseline (for raw values only), Week 6 and Week 12 of injection cycle 1, re-injection cycle visit, Week 6 and Week 12 of injection cycle 2, and last study visit.

# • Physiotherapist's belief that the GSC will help to improve functional capacity

Summary statistics (including the two-sided 95% CI) will be presented for raw scores and changes from baseline at each relevant visit: baseline (for raw values only), Week 6 and Week 12 of injection cycle 1, re-injection cycle visit, Week 6 and Week 12 of injection cycle 2, and last study visit.

• Subject compliance with the GSC

Summary statistics (including the two-sided 95% CI) will be presented for the percentage of days over study period when GSC therapy was performed in percentage. A frequency table of the percentage of days over study period when GSC therapy was performed in classes will also be provided with the two-sided 95% CI.

# Global assessment of benefits

Summary statistics (including the two-sided 95% CI) and frequency tables for both the investigator and the subject will be presented for raw scores at the re-injection cycle visit and last study visit.

• Satisfaction with longer interval between 2 injections

A frequency table of the satisfaction (including the two-sided 95% CI) with longer interval between 2 injections at the re-injection cycle visit and last cycle will be provided in subjects with an injection planned at Week 16 or 20 of each cycle.

A shift table comparing the satisfaction with longer interval between 2 injections between the two visits will also be provided in subjects with an injection planned at Week 16 or Week 20 of the two cycles.

• Quality of life changes, measured using the EQ-5D-5L and SF-12 scales

Summary statistics (including the two-sided 95% CI) will be presented for raw scores at baseline and last study visit, as well as for the changes from baseline at last study visit.

For each analysed score from EQ-5D-5L and SF-12 questionnaires, the change from baseline between the upper limb and the lower limb as primary TT will be analysed at last study visit using the same model as AROM against 10 prespecified muscle groups. As the index score is available for the French centers and the US centers only, the country which will be used as reference level in the model to compare the two countries will be the United States.

# 3.2.1.3 Exploratory efficacy analysis

The correlation between full composite AROM and active function (MFS (Local and central review) in UL and WS in LL) will be evaluated using correlation coefficients and their associated p-values. For each correlation (full composite AROM in UL and MFS (Local) / full composite AROM in UL and MFS (Central review) / full composite AROM in LL and WS), the correlation coefficient will be calculated on the changes from baseline and, at Week 12 of each injection cycle and last study visit. Depending of the normality of the two parameters analysed, the Pearson's correlation coefficient or the Spearman's correlation coefficient will be used.

The following SAS® code will be used:

PROC CORR data = *table* pearson spearman;

BY avisitn;

VAR chg\_fcXaroms chg\_mXXXX;

RUN;

The scatter plot of change from baseline of the full composite AROM in upper limb versus the change from baseline of the MFS overall score (Local and central review) will be presented at Week 12 of each injection cycle and last study visit on the same graph.

The scatter plot of change from baseline of the full composite AROM in lower limb versus the change from baseline of the maximal WS barefoot will be presented at Week 12 of each injection cycle and last study visit on the same graph.

## 3.2.2 Safety

All safety data will be included in the subject data listings for the Enrolled population and summary tables will be based on the safety population.

3.2.2.1 Adverse events

All AEs will be coded according to the Medical Dictionary for Regulatory Activities (MedDRA) Version in force within Ipsen at the time of first coding.

Listings will be presented and sorted by country, centre, subject ID, start date/time of AEs, primary system organ class, preferred term and verbatim text for all adverse events recorded during the study.

Listings of SAEs, AEs leading to withdrawal and listing of deaths will also be presented.

TEAEs will be flagged (\*) in the adverse events listing and will be summarised.

A TEAE is defined as any AE that occurs during the active phase of the study if:

• it was not present prior to receiving the first dose of IMP, or

it was present prior to receiving the first dose of IMP but the intensity increased during the active phase of the study.

An overall summary table of all AEs will be presented.

TEAEs will be summarised with the number and percentage of subjects with adverse events classified by primary system organ class and preferred term. The number of occurrences of a TEAE will also be presented.

In addition, summary tables will also be presented for:

- SAEs,
- Non serious TEAEs,
- TEAEs per decreasing frequency,
- TEAEs by maximum intensity,
- TEAEs by most serious causality,
- TEAEs associated with withdrawals,
- TEAEs of special interest by type of adverse events of special interest (AESI) (Hypersensitivity and Remote spread).

The list of MedDRA PTs and/or Standardised MedDRA Queries (SMQs) used to retrieve a list of potential AESIs of each type of specific events is detailed in Appendix 2.

In the event of multiple reports of the same event being reported by the same subject during the study, the maximum intensity (severe > missing > moderate > mild) and the most serious causality (related > not related) will be chosen.

## 3.2.2.2 Laboratory data

Not applicable for the study.

3.2.2.3 Vital signs

Vital signs will be listed at each assessment by country, centre and subject ID. Any unscheduled vital signs will be flagged [U] in the listing.

The baseline will be defined as the last available (and reliable if applicable) assessment collected prior to IMP administration, i.e. at the Baseline Visit (Cycle 1). Summary statistics (including the two-sided 95% CI) will be presented at each scheduled assessment for raw values and changes from baseline of blood pressure, heart rate, weight and Body Mass Index (BMI).

## 3.2.2.4 ECG

Not applicable for the study.

3.2.2.5 Physical examination

A listing with the date of test will be provided by country, centre, subject ID and visit.

# 3.2.3 Missing data and outliers

3.2.3.1 Missing data

Unless stated otherwise, no missing value will be replaced.

If a value required a retest, the last reliable non-missing value will be taken into account if measured before the administration of IMP; and the first non-missing

reliable value for post-baseline assessments. An assessment will be considered reliable if it is performed without any technical problem and if the result is within the range of plausible values. Any retest or unscheduled assessments performed will be included in the individual subject data listings.

If there is a significant number of missing values for a subject (or if there is confirmed data appearing spurious), a decision will be made following consultation with the sponsor regarding the handling of these data in summaries, during the Data Review Meeting.

## 3.2.3.2 *Missing or incomplete dates*

In all listings, missing or incomplete dates should be left as they have been recorded. However, for calculation / sorting / assignation based on dates, the following methods will be used.

For the calculation based on dates of the medical history, medications, non-drug therapies and adverse events, the missing/incomplete dates will not be replaced but the following rules will be applied:

- The most conservative approach will be systematically considered (i.e. if the onset date of an AE / concomitant medication is missing/incomplete, it is assumed to have occurred during the study treatment phase (i.e. a TEAE for AEs) except if the partial onset date or other data [stop date, ...] indicates differently).
- A missing/incomplete date of medical history will be assumed to have occurred before any study treatment.
- If a partial date and the associated information do not allow the assignation to a group/category, all the possible groups/categories will be considered (i.e. a medication with partial start and stop dates could be considered as prior and concomitant treatment).
- Where this is possible, the derivations based on a partial date will be presented as superior inequalities (i.e.: for an AE started in FEB2004 after the administration performed on 31JAN2004, the days since last dose will be "≥2", similarly the duration of ongoing AEs or medication will be "≥xx" according to the start and last visit dates).

For the calculation based on the date of ABI or the date of spasticity, the following rules will be applied:

- In the case of completely missing date, it will be estimated by the date of baseline visit.
- If the day and the month are missing:
  - If the year is the same as the year of baseline visit, it will be estimated by the date of baseline visit.
  - If the year is prior to the year of baseline visit, it will be estimated by the 31DECYYYY.
- If only the day is missing:
  - If the month and the year are the same as the month and the year of baseline visit, it will be estimated by the date of baseline visit.
  - If the month and the year are prior to the month and the year of baseline visit, it will be estimated by the last day of the month.

For the calculation based on the date of first BoNT injection before the study, the following rules will be applied:

- In the case of completely missing date, the date will remain missing and it will be assumed to have occurred before any study treatment.
- If the day and the month are missing:
  - If the year is the same as the year of date of last BoNT injection, it will be estimated by the date of last BoNT injection.
  - If the year is prior to the year of date of last BoNT injection, it will be estimated by the 31DECYYYY.
- If only the day is missing:
  - If the month and the year are the same as the month and the year of date of last BoNT injection, it will be estimated by the date of last BoNT injection.
  - If the month and the year are prior to the month and the year of date of last BoNT injection, it will be estimated by the last day of the month.

For the calculation based on the date of last BoNT injection before the study, the following rules will be applied:

- In the case of completely missing date, it will be estimated by the baseline visit.
- If the day and the month are missing:
  - If the year is the same as the year of date of first BoNT injection, it will be estimated by the date of first BoNT injection.
  - If the year is after the year of date of first BoNT injection, it will be estimated by the 01JANYYYY.
- If only the day is missing:
  - If the month and the year are the same as the month and the year of date of first BoNT injection, it will be estimated by the date of first BoNT injection.
  - If the month and the year are after the month and the year of date of first BoNT injection, it will be estimated by the first day of the month.

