4 SELECTION AND WITHDRAWAL OF SUBJECTS

4.1 Inclusion Criteria

All subjects must fulfil all of following criteria to be included in the study:

- (1) Subjects aged at least the national legal adult age.
- (2) Subjects with hemiparesis due to ABI (i.e. stroke or Traumatic Brain Injury (TBI)) presenting with muscle overactivity impeding motor function based on investigator's judgement including, but not limited to, at least one of the following requiring BoNT treatment: typical clenched fist; flexed wrist; flexed elbow; or plantar flexed foot.
- (3) At least 12 months since the ABI.
- (4) Naïve or non-naïve to BoNT treatment; if non-naïve, at least 4 months after the last BoNT injection, of any serotype.
- (5) Upper limb active function with an overall score between 2 and 7, as assessed by MFS locally rated score, if the primary TT limb is the UL.
- (6) A 10-metre maximal WS barefoot between 0.2 and 1.4 m/s, if the primary TT limb is the LL. Maximal WS barefoot will be performed preferably without walking aids. However, a cane may be permitted if absolutely necessary (although this may prevent detection of treatment-induced improvements). In this case, the same aid will have to be used for all WS assessments during the study.
- (7) Subjects must provide written informed consent to participate in the study prior to any study-related procedures.
- (8) Female subjects of childbearing potential (not surgically sterile or 2 years postmenopausal) must use a medically accepted method of contraception and must agree to continue use of this method for the duration of the study until the last visit of the subjects and for at least 12 weeks post injection. Acceptable methods of contraception include total abstinence, male partner has had a vasectomy, double barrier method (e.g. male condom plus spermicide, or female diaphragm plus spermicide), intrauterine device, or hormonal contraceptive (oral, transdermal, implanted and injected)..
- (9) Subjects must be willing and able to comply with study restrictions and to remain at the clinic for the required duration during the study period and willing to return to the clinic for the follow-up evaluation as specified in the protocol.

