# 3.2.6.1 Demographic data

The following demographic data will be summarized:

- Age: in years and in classes (<65 years /  $\geq$ 65 years)
- Sex (Male / Female)
- Race (Asian / Black or African American / White / Native Hawaiian or Other Pacific Islander / American Indian or Alaska Native / Other), except for French centers
- Ethnicity (Hispanic/Latino / Not Hispanic/Latino), except for French centers
- Height (cm)

- Body weight (kg) at baseline
- BMI (kg/m^2) at baseline
- Country (France / Czech Republic / Russia / USA)
- Selection of primary TT limb (UL / LL): this variable will be described overall and by country.
- Naïve to BoNT treatment (for UL and/or LL spasticities) (Yes / No)
- Naïve to GSC (Yes / No).
- 3.2.6.2 Other baseline characteristics

The following other baseline characteristics will be summarized:

- Disease history
  - Type of ABI (Brain trauma / Vascular (infarct or haemorrhage))
  - Duration since the date of ABI: in months and in classes ([12;18[ months / [18;24[ months / ≥24 months)
  - Time from spasticity onset: in months and in classes ([0;6[ months / [6;12[ months / [12;18[ months / [18;24[ months / ≥24 months)
  - Time between spasticity and first BoNT injection (first injection before the study for the non-naïve subjects and first injection in the study for the naïve subjects): in months and in classes ([0;6[ months / [6;12[ months / [12;18[ months / [18;24[ months / ≥24 months)
- Previous BoNT injections
  - For UL spasticity and for LL spasticity separately
    - BoNT treatment (naïve / non-naïve)
    - For non-naïve subjects to BoNT treatment: time from the first 0 BoNT injection ([0;6[ months / [6;12[ months / [12;18[ months / [18;24] months /  $\geq$ 24 months), time from the last BoNT injection ([0;6[ months / [6;12[ months / [12;18[ months / [18;24[ months / >24 months). brand name at the last injection (AbobotulinumtoxinA - DYSPORT® / OnabotulinumtoxinA -BOTOX® / IncobotulinumtoxinA - XEOMIN® or XEOMEEN® / Other) and, the time from the last BoNT injection and the total dose administered of the last injection (units) by brand
  - For non-naïve subjects previously treated with BoNT for UL and/or LL spasticity: total dose administered of the last injection (units) by brand
  - GSC
    - For non-naïve subjects to GSC only: subject satisfaction with GSC at baseline (Completely satisfied / Rather satisfied / Neither satisfied nor dissatisfied / Rather dissatisfied / Completely dissatisfied).

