### (18) Time between spasticity and first BoNT injection

The time between spasticity and first BoNT injection will be calculated as ((date of first BoNT injection – onset date of spasticity) + 1)/30.4375 and presented in months. The date of first BoNT injection will be the date of first BoNT injection before the study for the non-naïve subjects and the date of first BoNT injection in the study for the naïve subjects.

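### For subjects with missing dates, the SAP's imputation rules can give durations that are impossible for an eligible subject: 0.03 months since brain injury or last toxin, and negative times from spasticity to first toxin

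*SAP*

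**What the plan says.** SAP 3.2.3.2 sets separate rules for three kinds of date.

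- **ABI and spasticity onset.** The rules open with "For the calculation based on the date of ABI or the date of spasticity, the following rules will be applied". A wholly missing date goes to baseline: "In the case of completely missing date, it will be estimated by the date of baseline visit". With only the year known: "If the year is prior to the year of baseline visit, it will be estimated by the 31DECYYYY". With only the day missing and an earlier month, the date goes to the end of that month.
- **Last toxin injection before the study.** "In the case of completely missing date, it will be estimated by the baseline visit". Partial dates go to 1 January, to the first of the month, or to the first-toxin date.
- **First toxin injection before the study.** A wholly missing date stays missing. Partial dates go to 31 December, month-end or the last-toxin date.

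Protocol 4.1 requires "At least 12 months since the ABI" and, for toxin, "if non-naïve, at least 4 months after the last BoNT injection, of any serotype".

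SAP 3.2.6.2 reports "Duration since the date of ABI: in months and in classes", the lowest class starting at 12 months. Its classes for time from last toxin and for time from spasticity to first toxin start at 0. Appendix 1 (16), (18) and (19) give the formulas.

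**The concern.** An imputation rule should not produce a value that the entry criteria or the order of events exclude. Nothing in SAP 3.2.3.2 ties an imputed ABI date to the 12-month criterion or an imputed last-toxin date to the 4-month criterion, and nothing requires onset to precede a recorded first injection. The section is also uneven: a missing first-toxin date is left missing, while a missing last-toxin date becomes the day of the baseline visit.

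In a single-arm study, readers judge the response rate partly by who was treated, so chronicity and prior toxin exposure should be described correctly. The risks are impossible minima, subjects who fit no class, and a false recent-toxin value that looks ordinary in its class.

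**Working it through.** The SAP prints no figure for these durations, so there is none to reproduce. The rules come from SAP 3.2.3.2, the formulas from SAP Appendix 1, the entry limits from Protocol 4.1 and the classes from SAP 3.2.6.2. The calendar dates below are assumptions for illustration, with baseline 15 June 2017 unless stated.

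**Formulas, in months**

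- (16) since ABI = (baseline − ABI date + 1)/30.4375
- (19) since last toxin = (baseline − last-toxin date + 1)/30.4375
- (18) spasticity to first toxin = (first-toxin date − onset date + 1)/30.4375. "The time between spasticity and first BoNT injection will be calculated as" this difference, using the pre-study first injection for non-naive subjects and the in-study one for naive subjects.

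**Date wholly missing**

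- ABI: (0 + 1)/30.4375 = 0.03, against at least 12. No class holds it.
- Last toxin: (0 + 1)/30.4375 = 0.03, against at least 4. It falls in the [0;6[ class, where it looks like any other value.
- Onset missing, non-naive, first toxin 15 June 2015: (−731 + 1)/30.4375 = −23.98. No class holds it.
- Onset missing, non-naive, first toxin 15 February 2017 (four months before baseline): (−120 + 1)/30.4375 = −3.91.
- Onset missing, naive, injected on the day of the baseline visit: 0.03, which is not negative.

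**Date partial**

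- ABI known only as 2016, so set to 31 December 2016: (166 + 1)/30.4375 = 5.49. A subject injured by 15 June 2016 was eligible. With baseline on 2 January 2017 the same rule gives 3/30.4375 = 0.10; with baseline on 30 December 2017 it gives 365/30.4375 = 11.99.
- ABI truly 10 June 2016: (370 + 1)/30.4375 = 12.19. With the day missing it becomes 30 June 2016: (350 + 1)/30.4375 = 11.53.
- Onset known only as 2015, first toxin 1 July 2015: (−183 + 1)/30.4375 = −5.98.
- Onset March 2015 with the day missing, first toxin 10 March 2015: (−21 + 1)/30.4375 = −0.66.
- Last toxin February 2017 with the day missing, so set to 1 February: (134 + 1)/30.4375 = 4.44. The partial rules for this date move it earlier, so they do not breach the 4-month limit for an eligible subject.

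**The case against.** Several arguments on the other side carry weight.

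- **Rarity.** The ABI and last-toxin dates underlie two entry criteria and are required baseline items, so wholly missing values are probably few. This is reasonable, but a site can confirm more than 12 months from a year or an approximate history, and the SAP itself provides for wholly missing and year-only dates.
- **Existing safeguards.** SAP 3.2.3.3 excludes impossible or implausible outliers found before database lock, and SAP 3.2.3.1 sends spurious data to the Data Review Meeting. This is a partial answer. The planned outlier search covers range of motion, the Modified Frenchay Scale, walking speed, EQ-5D-5L, SF-12 and vital signs; it does not list these derived durations.
- **No effect on conclusions.** This stands. The durations do not enter the primary endpoint, the logistic model, the ANCOVA or the subgroups, and naive status rests on prior treatment, not on dates (Appendix 1 (14)).

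A reader might infer two stronger claims that the documents do not support. One is that the rules shorten every duration. Partial last-toxin dates move earlier, which lengthens time since last toxin, and partial first-toxin dates move later, which lengthens time from spasticity to first toxin. The other is that eligible subjects would be counted as entry violations. Eligibility is checked at the Baseline Visit (Protocol 5.2.1.1), unmet criteria have their own listings (SAP 3.2.4), and listings keep incomplete dates as recorded (SAP 3.2.3.2). Nothing derives eligibility, deviations or the per-protocol population from an imputed date.

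**Conclusion.** The rules are wrong as written, at the lowest severity. For an eligible subject, a wholly missing ABI or last-toxin date certainly gives an impossible value. A wholly missing onset certainly gives a negative value for a non-naive subject whose first-toxin date is usable. Partial ABI and onset dates fail only for some combinations of dates. For an enrolled subject who did not meet the criteria, a short interval could be true.

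The effect is confined to tables 14.1.5.2.1 and 14.1.5.2.2, with their mITT counterparts if produced. Its size cannot be stated, because the documents give neither the number of missing dates nor mean chronicity. As an illustration only, assume a true mean of 60 months since ABI, the same in subjects with and without a date. If a share f of dates is wholly missing, the reported mean is 60(1 − f) + 0.03f: 59.4 at 1%, 58.8 at 2% and 57.0 at 5%. The impossible minima and the unclassifiable subjects matter more than this shift.

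**What to change.** Amend SAP 3.2.3.2 as follows.

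1. Leave wholly missing ABI, spasticity-onset and last-toxin dates missing, as for the first-toxin date, and report the number missing for each.
2. For a partial ABI date, use the earlier of the current imputed date and baseline minus 12 months, provided that date lies within the recorded month or year. Otherwise keep the current imputed date, so that a recorded violation stays visible. With baseline 15 June 2017, an ABI recorded as 2016 or as June 2016 becomes 15 June 2016, giving (365 + 1)/30.4375 = 12.02 months. An ABI recorded as October 2016 stays at 31 October 2016, giving (227 + 1)/30.4375 = 7.49 months.
3. For a partial onset date, impute no later than the first-toxin date, again only within the recorded month or year. Onset 2015 with first toxin 1 July 2015 then gives (0 + 1)/30.4375 = 0.03 months, which falls in the [0;6[ class.

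The partial last-toxin rules can stay as they are; a 4-month bound would change nothing for eligible subjects. Item 2 leans on the eligibility check at baseline: where only the year is known and that year spans the 12-month limit, it assumes the subject met the criterion, and a footnote should say so.

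The cost is a few sentences in the SAP and a small change to the date derivations. No new data are needed.
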